9.9 Pooling of centers

Data will be pooled across centers. The "center" factor will not be considered in statistical models due to the high number of participating centers in contrast to the anticipated small number of participants per center.

9.10 Significance level

No statistical tests will be performed for any of the study endpoints. For descriptive purposes, 95% (CIs) or 90% CIs will be calculated where indicated.

9.11 Presentation of continuous and qualitative variables

Continuous variables will be summarized using descriptive statistics i.e. number of non-missing values and number of missing values [i.e. n (missing)], mean, median, standard deviation (StD), Q1, Q3, minimum (min), and maximum (max).

Qualitative variables will be summarized by counts and percentages. Unless otherwise stated, the calculation of proportions will be based on the number of participants of the analysis set of interest. Therefore, counts of missing observations will be included in the denominator and presented as a separate category.

In case the analysis refers only to certain visits, percentages will be based on the number of participants still present in the trial at that visit, unless otherwise specified.

Unless otherwise specified, time to event endpoints will be presented in months. Summary statistics will be reported with 1 digit.

9.12 Reporting conventions

Mean, median, Q1, Q3, Min, Max will have the same precision as SDTM data (number of digits) for non-derived data, and StD should be displayed to one digit more than the mean. Statistics on derived data will be rounded to reasonable digits, whereas maximal digits should be available in CDISC ADaM data sets. Percentages will be reported to one decimal place. The rounding will be performed to the closest integer / first decimal using the common mid-point between the two consecutive values. For example, 5.1 to 5.4 will be rounded to an integer of 5, and 5.5 to 5.9 will be rounded to an integer of 6.

9.13 Preferred term for analysis of WHO-DD coded data

For data coded according to WHO-DD (e.g., concomitant medications), summaries will be done on the preferred term level where the preferred term is corresponding to codes ending in 01001. With this approach, variations of salt forms of active ingredients will be analyzed under the same term, e.g. diphenhydramine and diphenhydramine hydrochloride will be analyzed as the same preferred term diphenhydramine.

9.14 Re-screened participants

Re-screened participants will be only counted once in the screening analysis set, considering the latest screening (screening with latest informed consent).

9.15 Data collected after re-initiated treatment

No re-initiation of treatment has been observed in this study at the time of cut-off date.

9.16 Categorization of participants for COVID-19 impact assessment

For the assessment of COVID-19 impact on this study, participants will be categorized as being affected by COVID-19 (either due to infection or due to circumstances of social distancing affecting the capabilities of sites/hospitals etc.) based on the COVID-19 study period defined as:

- The start of COVID-19 study period will be defined by country as the minimum of the date of the first death from COVID-19 occurred in each country according to the published data by European Centre for Disease Prevention and Control on 26 June 2020 and 11 March 2020 (WHO-start of world-wide pandemic).
- Post-pandemic could be defined as date (1) vaccination is released, (2) WHO declares COVID-19 pandemic over, (3) region-specific calls are made to end social distancing measures with no relevant rise in cases thereafter. As study treatment for the last participant started on 24 August 2017, no participant will be grouped into the post COVID-19 study period for this study and no post-pandemic date will be defined.

Participants will be categorized into subgroups as follows:

- Pre: Participant started treatment prior to COVID-19 study period
- During: Participant started treatment during the COVID-19 study period
- Post: Participant started treatment post the COVID-19 study period

9.17 Software

All statistical analyses of efficacy and safety will be performed using SAS® Grid. The computer program Phoenix® WinNonlin® Version 6.4 or higher (Certara, L.P., Princeton, New Jersey, USA) will be used for non-compartmental analysis of PK data, CCI

The same version of SAS as above will be used for PK/CCI data statistical analyses and outputs.

10 Study Participants

10.1 Disposition of Participants and Discontinuations

Analysis sets: Screening analysis set

The following parameters will be summarized by all cohorts combined (where applicable) and by cohort. This summary will be presented for all participants.

- Total number of participants screened overall
- Total number of re-screened participants
- Number of participants who discontinued from the trial prior to first dose of treatment
- Reason for discontinuation of trial prior to first dose of treatment (did not meet eligibility criteria, withdraw of consent, other)
- Number of participants who received no treatment
- Number of participants who received at least 1 dose of trial treatment (Safety Analysis Set)
- Number of participants with treatment on-going
- Number of participants who completed the treatment
- Number of participants who discontinued the treatment
- Number of re-initiated participants
- Reasons for treatment discontinuation
 - o Adverse event (AE)
 - Lost to follow-up
 - o Protocol non-compliance
 - o Death
 - o Progressive disease
 - Withdrew consent
 - o Other
- Number of participants who discontinued the treatment but are still in study for follow-up
- Number of participants who discontinued from the study
- Reasons for study discontinuation
 - Lost to follow-up
 - o Death
 - Withdrew consent
 - o Other

In addition, the number of participants in each analysis set defined in Section 8.1 will be summarized. The percentage of participants will be calculated based on the number of participants in the SAF population.

The follow-up time will be defined as the time between the date of first dose and the last known alive date of the subject (or cut-off date). Descriptive statistics will be provided. In addition, a Kaplan-Meier analysis will be performed using overall survival data by reverting the censoring flag (subjects still alive are counted as events, dead subjects are counted as censored).

10.2 Protocol Deviations

Analysis set: Full Analysis Set

10.2.1 Important Protocol Deviations

Important protocol deviations (IPDs) are protocol deviations that might significantly affect the completeness, accuracy, and/or reliability of the study data or that might significantly affect a participant's rights, safety, or well-being.

The following, but not limited to, are defined as important protocol deviations:

- Subjects that are dosed on the study despite not satisfying the inclusion criteria or meeting the exclusion criteria
- Subjects that develop withdrawal criteria whilst on the study but are not withdrawn
- Subjects that receive an incorrect dose
- Subjects that receive an excluded concomitant medication
- Deviation from Good Clinical Practice

IPDs will be identified for all participants by either site monitoring, medical review processes or programming and confirmed prior to or at the Data Review Meeting at the latest.

All IPDs will be documented in SDTM datasets whether identified through site monitoring, medical review or programming.

Frequency table per reason of important protocol deviations will be presented.

Important protocol deviations will also be presented in a data listing. This listing will include dose level/cohort, the participant identifier, age, sex, a category of the deviation (e.g. inclusion/exclusion), and a description of the deviation.

Important protocol deviations are specified in Appendix 1.

The number of participants with important protocol deviations overall as well as important protocol deviations due to COVID-19 will be tabulated. A listing of all COVID-19 Related Protocol Deviations (minor or important) will be provided. A listing of participants with any missed tumor assessments, missed samples/procedures and missed visits due to COVID-19 will

also be provided. The listing will be based on the COVID-19 protocol deviations included in CTMS, as well as the information recorded in the exposure eCRF page, if any.

11 Demographics and Other Baseline Characteristics

Demographics and other baseline characteristics will not be analyzed as there no change compared to CSR is expected.

12 Previous or Concomitant Medications/Procedures

Analysis set: Full Analysis Set

All Previous and Concomitant medications descriptions will be provided per dose level/cohort and overall (dose escalation overall, HCC overall, dose expansion overall [excluding HCC]).

12.1 Previous and concomitant medications

Pre-ICF medications are medications, other than study medications, which were taken within 30 days prior to signing the informed consent and were stopped prior to the signing of the informed consent.

Previous medications are medications, other than study medications and pre-medications for study drug, which are started before first dose date of study treatment. Pre-ICF medications which continue past the time of signing the informed consent will be categorized as previous medications. In case the date values will not allow to unequivocally allocate a medication to previous medication the medication will be considered as previous medication.

Concomitant medications are medications, other than study medications and pre-medications for study drug, which are taken by participants any time on-trial (on or after the first day of trial drug treatment for each participant) or within 30 days after last dose of trial drug OR the earliest date of subsequent anti-cancer drug therapies minus 1 day, whichever occurs first. In case the date values will not allow to unequivocally allocate a medication to concomitant medication the medication will be considered as concomitant medication.

Post follow-up medications are medications, other than study medications and pre-medications for study drug, which are started on or 30 days after last dose of trial drug OR on or after the earliest date of subsequent anti-cancer drug therapies, whichever occurs first.

Previous and Concomitant treatments will be summarized separately from the "Concomitant Medications Details" eCRF page. These summaries will present the number and percentage of participants by drug class and preferred term, overall and by dose level/cohort. Drug class will be derived as ATC classification Level 2, and the preferred term will be taken as the preferred drug name, based on the most recent available version of the WHO-DD dictionary. If multiple ATCs are assigned to a drug, all ATCs for that drug will be reported. A participant will be counted only once within a given drug class and within a given drug name, even if he/she received the same medication at different times. The summary will be sorted by ATC-2nd Level and Preferred Term in alphabetical order.

Pre-ICF, previous, and concomitant medications will be presented in separate listings. Pre-ICF medications will come from the "Relevant Previous Medications" eCRF page. Each listing will include dose level/cohort, participant identifier, age, sex, preferred term, medication name, start date, end date, dose, dose units, frequency, route, reason for the medication, and adverse event (if reason for medication was an adverse event). The drug class and the preferred term use for Pre-ICF medications will follow the same rules for previous and concomitant medications described in previous paragraph.

12.2 Premedications

Premedications for study drug are medications e.g. diphenhydramine or acetaminophen, which are administrated the same day as, but prior to the study drug administration to mitigate potential infusion-related reactions.

The number of participants receiving pre-medication will be summarized for each treatment visit based on "Premedication details" eCRF page (participants for whom the question "Has the participant received any pre-medications before MSB0011359C infusion?" is answered "Yes" at the corresponding visit).

A listing will be reported with the relevant information collected on the "Premedication Details" eCRF page. The listing will include dose level/cohort, participant identifier, age, sex, preferred term, reported medication name, date/time of administration, dose, dose units, and route.

12.3 Concurrent procedures

All concurrent procedures, which were undertaken any time during the on-treatment period, will be presented in a listing with information collected from the "Concomitant Procedures Details" eCRF page. Concurrent procedures will be classified by medical review. Procedures will be coded using current version of Medical Dictionary for Regulatory Activities (MedDRA) and reported using preferred term (PT).

Number of participants with concurrent procedures (Prior to first dose of trial treatment, and during on-treatment period) will be described.

Concurrent procedures will be presented in a listing will include dose level/cohort, participant identifier, age, sex, name of procedure, preferred term, start date, end date, and reason for procedure.

12.4 Subsequent Anticancer Therapies

Anti-cancer treatment after discontinuation of bintrafusp alfa will be provided in a data listing with data retrieved from "Anti-Cancer Treatment After Discontinuation Details", "Radiotherapy After Discontinuation Details", and "Surgery After Discontinuation Details" eCRF pages.

The number of participants in each of the following anti-cancer treatment categories will be tabulated, all dose level/cohorts combined (where applicable), and by dose level/cohort:

- Participants with at least one subsequent anti-cancer treatment (i.e. therapy, radiotherapy or surgery)
- Participants with at least one subsequent anti-cancer drug therapy
- Participants with at least one subsequent anti-cancer radiotherapy
- Participants with at least one subsequent anti-cancer surgery

The type of subsequent anti-cancer drug therapy as provided in the e-CRF (i.e. anti-PD-1/anti-PD-L1, cytotoxic therapy, endocrine therapy, monoclonal antibodies therapy, small molecules, immunotherapy except anti-PD-1/anti-PD-L1, other) will be described, as well as the best response across all post trial treatments (complete response, partial response, stable disease, progressive disease, non-complete response/non-progressive disease, not assessable, unknown, not applicable).

In addition, the anti-cancer treatment after discontinuation of bintrafusp alfa will be provided in a data listing including with relevant information.

The earliest date of start of new anti-cancer therapy after discontinuation of bintrafusp alfa will be used for the definition of the on-treatment period and censoring for efficacy analyses

13 Study Treatment: Compliance and Exposure

Analysis set: Safety Analysis Set

The following analyses will be performed based on the safety analysis set by dose level/cohort. All dosing calculations and summaries will be based on "MSB0011359C Administration Details" eCRFs page. A listing of study drug administration will be created with the information collected on the "MSB0011359C Administration Details" eCRF page.

Subjects will receive an IV infusion of bintrafusp alfa over 1 hour (-10 minutes / +20 minutes, that is, over 50 to 80 minutes) once every 2 weeks as detailed in the Schedule of Assessments in the study protocol.

After confirmation of tolerability at 20 mg/kg in the dose escalation part, the bintrafusp alfa dose for further investigation is 1200 mg for GC, ESCC, and BTC participants. Summary statistics for GC, ESCC, and BTC cohorts will be derived based on the flat dose.

The duration of bintrafusp alfa treatment (in weeks) during the study for a patient is defined as:

duration=
$$\left(\frac{\text{date of last dose-date of first dose+14}}{7}\right)$$

The cumulative dose of bintrafusp alfa per patient in a time period is the sum of the actual dose levels that the patient received within that period (i.e., total dose administered). The cumulative dose is expressed in mg/kg for dose escalation and HCC participants, and in mg for dose expansion participants excluding HCC participants.

The dose intensity (DI) and the relative dose intensity (RDI) will be calculated for each patient across all cycles. The dose intensity per cycle (mg/2 weeks) is defined as

$$DI = \left(\frac{\text{Cumulative dose}}{\text{treatment duration (weeks)/2}}\right)$$

The dose intensity is expressed in mg/kg/2 weeks for dose escalation and HCC participants, and in mg/2 weeks for dose expansion participants excluding HCC participants.

The relative dose intensity (RDI) is defined as the actual dose intensity divided by the planned dose intensity per cycle and expressed in percentage.

RDI (%)=
$$100 \times \left(\frac{\text{DI}}{\text{planned dose level}} \right)$$

- The summary of treatment exposure and compliance for bintrafusp alfa will include:
 - Duration of therapy (weeks)
 - Total number of infusions received
 - Cumulative dose (mg/kg or mg)
 - Dose intensity (mg/kg/2 weeks or mg/2 weeks)
 - Relative dose intensity (%) as continue variable, also categorized as
 - o < 80%
 - 0 80%-90%
 - o >90%

All descriptions will be provided per dose level/cohort and overall (dose escalation overall, HCC overall, dose expansion overall (excluding HCC)).

- Two listings will be presented for treatment exposure and compliance:
 - A listing of study drug administration will be created with the information collected on the "MSB0011359C Administration Details" eCRF page. This listing will include assigned dose level/cohort, participant identifier, age, sex, infusion start date/time, infusion end date/time, infusion rate (mL/hr), actual dose (mg or mg/kg), treatment administration modification (Y/N), modification details (infusion rate reduction/temporary interruption and time infusion resumed/discontinued at this visit), reason for administration modification (AE/other), and treatment delay (days). Body weight will also be displayed for participants from dose escalation and HCC subjects
 - A listing of treatment exposure and compliance will include assigned dose level/cohort, participant identifier, age, sex, duration of therapy (weeks), total number of infusions received, cumulative dose (mg or mg/kg), dose intensity (mg/2 weeks or mg/kg/2weeks), and relative dose intensity (%)

Dose Reductions

Dose reduction is not allowed per protocol and will not be summarized.

Dose Delays

Delays will be derived based on infusion date and will be based on the deviation of the actual to the planned treatment administration day (relative to the previous treatment administration date). A delay is defined as 1 day or more of delay between the actual and the planned treatment administration day. For example, if one participant receives bintrafusp alfa on day 1, then the next administration date will be on day 15; however, if the participant receives trial treatment on day 17, this will be considered as a delay of 2 days.

The following will be summarized in a table, overall and by dose level/cohort:

- Number of participants with at least one delay
- Number of delays per participant, categorized as $0, 1, 2, 3, \ge 4$
- Number of cumulative delay days per participant, categorized as $0, 1-2, 3-6, \ge 7$ days

Infusion Rate Reductions

Infusion rate reductions as recorded on the "MSB0011359C Administration Details" eCRF page will be used for analysis. Number of participants with at least one infusion rate reduction, number of participants with at least one infusion rate reduction due to adverse event, as well as a categorization of infusion rate reductions $(1/2/\ge 3)$ will be summarized.

Study Drug Temporary Interruptions

Study drug temporarily interrupted as recorded on the "MSB0011359C Administration Details" page of the eCRF will be used for analysis. Number of participants with at least one study drug interruption, number of participants with at least one study drug interruption due to adverse event, as well as a categorization of study drug interruptions $(1/2/\ge 3)$ will be summarized.

14 Efficacy Analyses

Analysis sets: Full Analysis set

The endpoint evaluation will be performed separately for each cohort.

Table 2 provides an overview of the tumor response endpoints per criteria.

Table 2 Overview of Tumor Response Endpoints

Endpoints	Escalation part	Expansion part (HCC Cohort)	Expansion part (GC, ESCC, BTC Cohorts)
BOR, Duration of Response (DR), PFS per	✓, by investigator	✓, by IRC (primary secondary)	✓, by IRC (primary secondary)

Endpoints	Escalation part	Expansion part (HCC Cohort)	Expansion part (GC, ESCC, BTC Cohorts)
RECIST 1.1	(secondary)	✓, by investigator (secondary)	✓, by investigator (secondary)
OS	✓, (secondary)	✓, (secondary)	✓, (secondary)

Of note, some endpoints in the Table 2 might not be analyzed using investigator assessment, but listings and/or graphs for investigator assessment will be provided.

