- a A time window of up to 3 days before or 1 day after the scheduled visit day (-3/+1 days) will be permitted for all procedures (except Day 2 and the Day 43-50 visit). The biweekly 14-day schedule should be strictly adhered to, returning to the target date even if the previous visit was off schedule. The Day 43-50 visit is to accommodate collection of tumor biopsy material and associated PK and CCI (see Table 3).
- b Subjects without progressive disease at End-of-Treatment visit will be followed up for disease progression (CT/MRI scans every 12 weeks) until PD. In addition, subjects will be followed every 12 weeks for survival (including assessment of any further tumor therapy). The survival follow-up will continue until 1 year after the last subject receives the last dose of trial drug. After completion of the Follow-up period the appropriate electronic Case Report Form section for Trial Termination must be completed.
- c Any subject who experiences an AE that mandates discontinuation of trial treatment should have a discontinuation visit within 7 days after the decision to discontinue trial treatment.
- d Tumor evaluation at the End-of-Treatment visit should only be performed if no disease progression has been documented previously. If another antineoplastic therapy is administered before the end of the 28-day period, the End-of-Treatment visit should be conducted before the start of new therapy if possible.
- e Assessments for skin lesions or rash with biopsy of suspicious lesions. Dermatological consults should be requested as needed.
- f ECG to be taken before dosing and as soon as possible after completion of the infusion. If only a single "X", then only ECG before dosing is required. All ECGs will be conducted according to local procedure and will NOT be digitally uploaded.
- Wital signs should be assessed predose (within 15 minutes of start of infusion), then every 15 (±2) minutes after the start of infusion, and 15 (±5), 30 (±5), 60 (±5), 120 (±10), and 360 (±150) minutes after the end of infusion for the first 2 infusions. If there were no clinically significant changes in vital signs during the first 2 infusions, then the vital signs schedule for subsequent infusions will be predose (within 15 minutes of start of infusion), 30 (±5) and 60 (-5/+15) minutes after the start of infusion, and 30 (±5), 60 (±10), 6

28/167

Global Version ID: CC

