Measure	Day -28 to First Treatment	D1	D2 ^{cc}	D8cc	D15	D22 ^{cc}	D29	D43	D43- 50 ^{cc}	D57	D71	D85	Until Progression	` '	(+/- 2 weeks)	Every 12 weeks (+/- 2 weeks)

ACTH=adrenocorticotropic hormone; ADA=anti-drug antibody; AE=adverse events; ANA=anti-nuclear antibody; β-HCG=β-human chorionic gonadotropin; CT=computer tomography; DLT=dose-limiting toxicity; EBV=epstein barr virus; ECG=electrocardiogram; ECOG PS=Eastern Cooperative Oncology Group Performance Status; EORTC QLQ-C30=European Organisation for Research and Treatment of Cancer Quality of Life Questionnaire Core instrument; EORTC QLQ-STO22=stomach cancer module; EORTC QLQ-OES18=esophageal cancer module; EORTC QLQ-BIL21=cholangiocarcinoma and gallbladder cancer module; EORTC QLQ-HCC18= hepatocellular carcinoma module; FSH=follicle stimulating hormone; HBV=hepatitis B virus; HCV=hepatitis C virus; HIV=human immunodeficiency virus; IMP=investigational medicinal product; MRI=magnetic resonance imaging; PD=progressive disease; PGIS=Patient Global Impression of Severity; PK=pharmacokinetics; RF=rheumatoid factor; SpO2=Oxygen saturation; TGFβ=transforming growth factor beta; TSH=thyroid stimulating hormone, T4=thyroxine.

Unless stated otherwise in a footnote, all procedures and samples should occur prior to trial drug administration.

- a A time window of up to 3 days before or 1 day after the scheduled visit day (-3 / +1 days) will be permitted for all procedures (except Day 2 and the Day 43-50 visit). The bi-weekly 14-day schedule should be strictly adhered to, returning to the target date even if the previous visit was off schedule. The Day 43-50 visit is to accommodate collection of tumor biopsy material and associated PK and CCI (see Table 3).
- Subjects without progressive disease at End-of-Treatment visit will be followed up for disease progression (CT/MRI scans every 12 weeks) until PD. In addition, subjects will be followed every 12 weeks for survival (including assessment of any further tumor therapy). The survival follow-up will continue until 1 year after the last subject receives the last dose of trial drug. After completion of the Follow-up period, the appropriate electronic Case Report Form section for Trial Termination must be completed.
- c Any subject who experiences an AE that mandates discontinuation of trial treatment should have a discontinuation visit within 7 days after the decision to discontinue trial treatment.

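### SAP section 13 counts dose delay from the previous actual dose with no tolerance, so dosing inside the protocol's -3/+1 day window is tabulated as delay

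*SAP*

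**What the plan says.** SAP section 13, under Dose Delays, derives delays from infusion dates as the "deviation of the actual to the planned treatment administration day (relative to the previous treatment administration date"). The threshold is: "A delay is defined as 1 day or more of delay between the actual and the planned treatment administration day". In its worked example, a subject dosed on day 1 is next due on day 15, and "if the participant receives trial treatment on day 17, this will be considered as a delay of 2 days". Three summaries follow: subjects with at least one delay, delays per subject (0, 1, 2, 3, 4 or more), and cumulative delay days (0, 1-2, 3-6, 7 or more).

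The protocol works from a fixed grid. Table 1 footnote a (dose escalation) gives "A time window of up to 3 days before or 1 day after the scheduled visit day" for all procedures except Day 2 and the Day 43-50 visit, and adds: "The biweekly 14-day schedule should be strictly adhered to, returning to the target date even if the previous visit was off schedule". Table 2 footnote a says the same for the expansion part: "The bi-weekly 14-day schedule should be strictly adhered to, returning to the target date even if the previous visit was off schedule". The window covers the infusion itself: the subject replacement rule in protocol 5.5.1 applies the same -3/+1 limits to drug administration in the DLT period.

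Protocol 8.5.5 lists the number of dose delays as an exposure measure but does not define a delay. The visit windows in SAP 9.6 serve by-visit safety analyses and leave the delay rule unchanged.

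**The concern.** The two documents use different reference points. The protocol asks the site to return to the target date after an early visit, which necessarily makes the next interval longer than 14 days. The SAP then scores that longer interval as a delay. The SAP also has no counterpart to the permitted +1 day, so a dose 1 day late is a delay whichever reference date is used.

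The measure matters because the protocol permits no dose reductions (5.1.7.1), which leaves delays as one of the few dosing signals of tolerability. The Safety Monitoring Committee is also to consider treatment-related events that delay dosing (protocol 2.2.1). SAP section 13 gives a separate count due to adverse events for infusion rate reductions and for interruptions, but none for delays. A reader of the delay table alone cannot tell a toxicity hold from a visit moved within the window.

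**Working it through.** **Rule.** For each dose after the first, SAP delay = max(0, actual day - (previous actual day + 14)). Early doses are taken as zero delay.

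**SAP example reproduced.** 17 - (1 + 14) = 2 days, as stated. Because it starts from day 1, this example cannot separate the two reference points. The SAP's parenthesis about the previous administration date does.

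**In-window schedules** (targets on days 1, 15, 29, 43, 57):
- Days 1, 12 (-3), 29 (on target): 29 - (12 + 14) = 3. An on-target dose becomes a 3-day delay.
- Days 1, 16 (+1): 16 - 15 = 1. A permitted dose becomes a 1-day delay.
- Days 1, 12, 30, 40, 58 (offsets 0, -3, +1, -3, +1): 30 - 26 = 4 and 58 - 54 = 4. This gives two delays and 8 cumulative days, the top cumulative category.

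Counting only doses later than target + 1 day gives zero in all three cases, and the SAP's day-17 example remains a 2-day delay.

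**Frequency.** The documents give no distribution of offsets, so this part is assumed. Take the first dose on day 1, every later dose in window and independent, 90% on target, and 2.5% at each of -3, -2, -1 and +1. No delay is scored only if offsets never increase from dose to dose. With m intervals,

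P(no delay) = sum over j = 0 to m of 0.9^(m-j) x 0.025^j x (j+1)(j+2)/2.

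- 4 doses, m = 3: 0.7290 + 0.0608 + 0.0034 + 0.0002 = 0.793, so 20.7% have at least one spurious delay.
- 7 doses, m = 6: 0.5314 + 0.0443 + 0.0025 + 0.0001 = 0.578, so 42.2%.
- 13 doses, m = 12: 0.2824 + 0.0235 + 0.0013 + 0.0001 = 0.307, so 69.3%.

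On schedule, the 4th, 7th and 13th doses fall on days 43, 85 and 1 + 12 x 14 = 169.

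**Top categories, same assumption.** At 4 doses there are only three intervals, so four delays are impossible. The most delay days possible is 5 (offsets +1, -3, +1). At 13 doses, 0.9% have four or more delays and 1.6% have seven or more delay days.

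**Sensitivity to the assumed offsets:**
- 7 doses, 70% on target (5/5/10/70/10% at -3/-2/-1/0/+1): 84.1% have at least one.
- 7 doses, all five offsets equally likely: 99.5% have at least one, 3% have four or more, and 10% have seven or more days.
- 13 doses, 80% on target: 92% have at least one and 9% have four or more.
- 13 doses, all offsets equally likely: 87% have four or more and 86% have seven or more days.

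**Which part of the rule is responsible.** With the fixed target as reference but still no window, only +1 doses count. At 7 doses and 2.5% at +1, that is 1 - 0.975^6 = 14.1%, against 42.2% under the SAP rule. Both the reference point and the missing window contribute.

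**The case against.** The best defence is that the SAP has chosen a definition rather than broken one. The protocol does not define a delay, and a 17-day gap is in fact 3 days longer than 14. Protocol 6.9 itself uses dose-to-dose intervals when defining non-compliance. That removes any charge that the SAP contradicts a protocol definition. It does not rescue the table, because the SAP calls the quantity a deviation from the planned day, and the protocol's planned day after an early dose is the target date.

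The interval rule also does two things well. If doses are given on days 1 and 15, held at 29 and resumed on 43, it scores 43 - (15 + 14) = 14 days. A bare grid of Day 1 plus multiples of 14, matched to the nearest date, would score zero. And a subject who slips 2 days once and then keeps 14-day intervals had one delay. Scored by dose number against a bare grid, 13 infusions would give 12 delays and 24 delay days. Both points stand and shape the fix.

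A reader might infer from the equal-offset scenario that the table would mainly measure visit variation. The documents do not support that. They give neither the offsets nor the number of true delays, and equal offsets sit badly with an instruction to adhere strictly to the schedule.

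Tolerability is also assessed elsewhere: DLTs and adverse events are the primary endpoints, and adverse events leading to interruption or discontinuation are tabulated (SAP 16.1.2). The planned listing of each infusion with its delay in days would allow a window to be applied afterwards.

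**Conclusion.** The concern holds for the delay table. That compliant dosing can be scored as delay follows from the stated rules by date arithmetic and needs no assumption. How often it happens cannot be known from the documents. With all doses in window and 90% on target, about 21%, 42% and 69% of subjects at 4, 7 and 13 doses have at least one spurious delay. At 13 doses about 1% reach four delays and 2% reach seven days. The row most affected is therefore subjects with at least one delay; the upper categories are materially affected only if in-window variation is much larger or treatment is long.

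It would be tempting to conclude that the trial's safety and tolerability findings are distorted. They are not: the table is descriptive, relative dose intensity is not built from the delay count, and no primary endpoint, efficacy result or sample size uses it.

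**What to change.** In SAP section 13, classify a dose as delayed only if it is given later than the protocol-scheduled day for that administration plus 1 day. Show in-window shifts in a separate row, or do not count them as delays. Two conventions need to be written down with it:
- A skipped or held administration still counts as a delay or missed dose and is not matched to the next grid date as if on time.
- A slip carried forward with 14-day intervals counts as one delay event, not a new one at each later dose.

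This changes the analysis only; no dosing rule is touched. Infusion dates are already collected.

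SAP section 6.1 records that the CSR and its addendum are approved and that there will be no final analysis, while section 4 foresees use of these analyses in submissions or manuscripts. Where the delivered table is reused, add the out-of-window row, or at least a footnote saying that delays are measured from the previous dose and include in-window shifts.

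The cost is a small derivation change and a rerun of one table, or a footnote alone. Reported delay counts will usually fall, so revised figures will not match those already delivered and should be labelled.
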